### **1. Research Title**

Comparison of Modified Circular and Natural Tooth Brushing Methods in Effectiveness of Dental Plaque Removal

### **3. Background information/Significance of Research Project**

Dental caries, or commonly known as tooth decay, is worldwide disease that pursues people during their lifetime (1). Dental caries can affect the health and quality of life patients so that it is important to focus on caries prevention (2). Ministry of Health Republic of Indonesia in Basic Health Research 2013 (3) showed that DMF-T Index of Indonesia for population aged start from 12 years old was 4.6. While the DMF-T Index in Yogyakarta province was 5.9, higher than the national index of DMF-T. Not only dental caries, gingivitis also being a problem. In Jakarta, 68% children aged 12 years old have gingivitis. While, 92% of the children aged 12 years old have substantial amount of plaque (4).

Both of dental caries and gingivitis are caused by dental plaque or known as dental biofilm. Gingivitis is built by the accumulated dental plaque that infect soft tissue around the teeth (5). Dental caries is caused generally by acid production from bacterial fermentation in the dental plaque on the tooth surface (6).

Dental caries and gingivitis can be prevented by plaque control. Self-performed mechanical plaque removal with a manual toothbrush remains the primary method of maintaining good oral hygiene for a majority of the population (7). Good oral hygiene habit that is built especially in children age will protect permanent teeth that can make it lasts a lifetime (8). Oral hygiene instructions should be given to a child considering their age and associated with their manual dexterity. Tooth brushing instruction can be effectively given in the age start from 10 years old because they can be actively involved and have better manual dexterity than children in younger age (9).

Ideal tooth brushing method is the method that can work for the individual and can remove dental plaque without causing damage on the teeth, gingiva, or other tissue

(10, 11). The method should clean all tooth surfaces and must be systematically organized so that each parts of the dentition is brushed (12, 13). Horizontal motions of brushing and parallel positions of the brush with the teeth will cause abrasion (14). Brushing force is not specifically determined. If it is too much, it will cause gingival trauma (15). Tooth brushing method that is ideal also has to be simple and easy to learn (12).

Tooth brushing will be effective in removing the dental plaque if it is done with the sufficient duration at least 2 minutes (16). Frequency of tooth brushing is recommended to be done twice a day (17). Tooth brushing type that is used to brush is recommended using manual tooth brush with small-headed toothbrush, soft round-ended filaments and comfortable handle (18). There are several factors from individual that may cause the differences in effectiveness of tooth brushing in plaque removal such as age, education, and socioeconomic status (13, 19, 20).

People, without any training, naturally brush their teeth using horizontal scrub, a rotary motion, or simple up and down (21). Many people using natural motion of tooth brushing can produce good oral environment that inhospitable to biofilm without any damaging effect in their tissue (21, 22). Asadoorian (15) estimated that over 90% of people employ their natural tooth brushing method that is personally built. This method will remove plaque from smooth surfaces of the teeth, but this method have limitation that is considered detrimental because it can cause gingival recession and tooth abrasion (23). People will pay poor attention to the lingual areas of their teeth while practicing this method probably because these areas do not affect the aesthetics and tend to difficult to be accessed (24).

A systematic review by Muller-Bolla and Courson (25) showed that in early mixed dentition stage, the most effective tooth brushing technique is horizontal technique. McClure (26) comparing tooth brushing efficacy between horizontal Scrub and modified Bass method in children aged 10-12 years old reported there were no significant differences in plaque removal ( $P > 0.01$ ) between two methods. Robinson (27) evaluated plaque removal of Scrub and Bass methods in children aged 12-13 years old and found that there were no differences between two methods. Smutkeeree et al. (28) found that there were no significant differences in gingival condition (Gingivitis Index) between Horizontal Scrub and Modified Bass groups ( $P > 0.05$ ) in children aged

10-12 years old. However, the studies about tooth brushing method recommended for children in late mixed dentition aged are still limited.

[figure not shown]
Children aged 10-12 years old are in late mixed dentition (29), a transitional period from children with milk teeth into adult with permanent teeth (30). Tooth brushing technique that is suitable for children should be simple to be performed so that it can be mastered by children and effectively remove dental plaque as well as prepare children for adult period and protect permanent teeth that can make it lasts a lifetime (8, 31). The review literature by Wainwright and Sheiham (32) showed that the Bass and modified Bass methods are the most frequently advocated method for adults. The Bass method showed a superiority in plaque removal ability compared with roll, circular, and horizontal method (33). The Bass method is good in cleaning the tooth tissue adjacent to the gingival tissue, the gingival margins and the gingiva sulcus (34). Nevertheless, this method is difficult to exercise (35). Katz et al. (36) recommended the Bass method to be combined with roll method to be the Modified Bass to ensure plaque removal from gingival margin and coronal surface. Modified Bass is effective in plaque removal of supragingival area (37). This method also can reduce chance of developing gingival recession and tooth abrasion (28). However, the Modified Bass method still have limitation that can cause difficulty in children to replace the brush in gingival sulcus position (5).

Combined tooth brushing technique can be considered as a good method for plaque removal (37). The combination should provide satisfactory method that should clean all tooth surfaces, the movement of the brush should not injure the soft and hard tissue, the technique should be simple and easy to learn, and it must be well organized so that each part of the dentition is brushed (12). In the Bass method originated by Bass (38), the brush need to be positioned at about a 45 degree to the long way of the teeth and then brush forced into crevices and moved short back and forth. Furthermore, most of people gradually switch from the correct Bass method with short stroke to be a horizontal scrubbing method as the interval since the instruction of the Bass method given (39). Eley et al. (12) in their book stated in different way that the Bass method should move with small circular motion and this combination can be recommended as the method of choice for general use. This method might be benefit for children in late mixed dentition because it does not need rolling motion like in the Modified Bass method that cause children difficult to replace in gingival sulcus position and the movement is not short

back and forth like in the original Bass method that children gradually switch from the correct Bass method with short stroke to be a horizontal.

*Delivering better oral health* (18) stated that there is no tooth brushing that is superior to another and people's existing method may need to be modified to clean all tooth surfaces. A study showed that different surface of the teeth need different technique to produce effective plaque removal (24). This study will apply the Modified Circular to be used in most of tooth surfaces areas as all labial areas, and posterior lingual/palatal areas and combine with vertical technique to be used in anterior lingual areas, and horizontal to be used in occlusal areas. To show the possibility that the Modified Circular method that can effectively remove plaque in late mixed dentition children, it is needed to comparing the Modified Circular method with the natural tooth brushing method.

#### 4. Conceptual Framework

## 5. Objectives

### General objectives

- a. To compare level of plaque of children aged 10-12 years old that use the Modified Circular method and natural tooth brushing method.
- b. To compare level of gingivitis of children aged 10-12 years old that use the Modified Circular method and natural tooth brushing method.

### Specific objectives

- a. To compare level of plaque before and after using the Modified Circular tooth brushing method.
- b. To compare level of gingivitis before and after using the Modified Circular tooth brushing method.

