#### Dependent Variables and Data Collection

The dependent variables in this study were Plaque Index (PI) and Gingival Index (GI). The hypotheses of this study were the plaque level and gingivitis level in subjects using the Modified Circular method is different from that in subjects using natural tooth brushing method and the level of plaque after using the Modified Circular method is different from that before using the method.

*Plaque Index Examination.* Participants' plaque level was measured using Turesky Modification of Quigley Hein (83). Data were collected during baseline and follow-up to track the changing of the plaque level before and after intervention. The tools used in this examination were micro-brush, mouth mirror and probe under the natural light. The procedure was painting all of the exposed tooth surfaces with disclosing solution and the participants were asked to rinse one time. Facial and lingual surfaces of the teeth were examined except third molars. A score between 0 and 5 was given based on the criteria. The plaque scores were recorded on the plaque index examination sheet containing the diagram of the teeth with the separated boxes of facial and lingual/palatal areas. The index was determined by calculating the total score divided by the numbers of the surfaces examined.

Table 1 Scoring criteria of Turesky Modification of Quigley-Hein Index (83)

Score	Criteria
0	No plaque.
1	Separate flecks of plaque at the cervical margin of the tooth.
2	A thin continuous band of plaque (up to one mm) at the cervical margin of the tooth.
3	A band of plaque wider than one mm but covering less than one-third of the crown of the tooth.
4	Plaque covering at least one third but less than two thirds of the crown of the tooth.
5	Plaque covering two-thirds or more of the crown of the tooth.

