#### Data collection procedure

- 1) The researchers well informed the teachers, parents or guardians, and the children about the purpose of the study, the procedure, and the right to continue or withdrawn without any penalties. The parents or guardians of the children who meet the inclusion criteria were asked by the researcher and teachers the permission to their children to participate in this study. Their consent were shown by signing of the consent form.
- 2) The appointment were made with the teachers to set the time to perform examination and intervention to the children.
- 3) Baseline data collection were done to all of the student participating of the study. The children were interviewed by interviewee using structured-questionnaire inside of the class. The oral examinations were done after completing the interview. The oral examination began with the examination of gingival condition and then continued with plaque level examination. Examination area was set outside of the class to get enough light. The children were examined on a chair in sitting position using natural sun light. The examiner was blind to the allocation of the group, the examiner will not know whether the group examined was intervention group or control group. After the oral examination was done, the video recording was taken to the children to record the way the children brush their teeth. The area recorded was only around their mouth and not showing their face.
- 4) In the other day, children in each group were given 2 hours for tooth brushing training course in small groups containing 4-5 children per group. The instructor motivated the children about how to improve oral hygiene for both groups. The

children were instructed to brush their teeth two times per day in two minutes. The control group were instructed to brush the teeth as how they brushed every day. The intervention group were demonstrated about how to brush the teeth using Modified Circular method. After the training in the class was completed, the activity then continued with practiced brushing together in schoolyard. Intervention group were observed once a week to make sure that they did Modified Circular method well without any repetition or addition of intervention. The researcher provided toothbrush and toothpaste to be used by the children during the one-month intervention period.

- 5) Follow up examination were done one month after the training by collecting the same data as baseline.

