## **7. Statistical analysis**

All of the data were analyzed using IBM SPSS Statistics 21. The data gathered from the control and the groups were compared using t-test for the mean and standard deviation. A chi-square statistic were used to investigate whether distributions of categorical variables differ from one another. The significance level used in this study was 0.05 for all of the statistical test.

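### The specific objectives and second hypothesis rest on before/after change in the Modified Circular arm alone, which is not evidence for the method because both arms shared several co-interventions

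*Combined protocol and SAP*

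**What the plan says.** The Specific objectives (Section 5) are "To compare level of plaque before and after using the Modified Circular tooth brushing method" and "To compare level of gingivitis before and after using the Modified Circular tooth brushing method". Neither mentions the control group.

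Dependent Variables and Data Collection (Section 6) states two hypotheses. The first is between arms: "the plaque level and gingivitis level in subjects using the Modified Circular method is different from that in subjects using natural tooth brushing method". The second is within one arm and covers plaque only: "the level of plaque after using the Modified Circular method is different from that before using the method". Specific objective b, on gingivitis, therefore has no matching hypothesis.

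The General objectives do use the control arm, for example "To compare level of plaque of children aged 10-12 years old that use the Modified Circular method and natural tooth brushing method", with a parallel objective for gingivitis.

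The Data collection procedure describes what the arms had in common: "children in each group were given 2 hours for tooth brushing training course in small groups", and "The instructor motivated the children about how to improve oral hygiene for both groups". It also tells the children, without limiting this to one arm, to brush twice daily for two minutes. Materials and Equipment says that every participant was given a brush and paste.

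On tests for means, Section 7 says only: "The data gathered from the control and the groups were compared using t-test for the mean and standard deviation". It names no paired test, change score or baseline adjustment.

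**The concern.** A before/after change in one arm is the sum of everything that happened to those children in the month. Here that includes motivation, a training course, advice on frequency and duration, new supplies and the knowledge of being examined again, as well as the brushing method. If the specific objectives and second hypothesis are answered by a significant within-arm change, a reader may credit the method with an improvement that the shared components could have produced alone.

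The Background section itself argues that showing the method's effectiveness requires comparing it with natural brushing. The specific objectives and second hypothesis leave that comparison out, although the control children had the same two examinations.

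**Working it through.** The documents give no effect size, SD, correlation or sample-size calculation, so there is no planned figure to reproduce. The stated arm sizes agree with the stated total: 62 + 62 = 124.

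**Which components are shared**

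| Component | Modified Circular arm | Control arm | Where stated |
|---|---|---|---|
| Motivation | yes | yes | Data collection procedure |
| Small-group training course | yes | yes | Data collection procedure |
| Twice daily, two minutes | yes | yes (stated for the children generally) | Data collection procedure |
| Brush and paste | yes | yes | Materials and Equipment |
| Baseline and one-month examination | yes | yes | Participants and setting; Data collection procedure |
| Specific method taught | yes | no | Experimental Design |
| Weekly reinforcement sessions | yes | no | Participants and setting |

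The first five rows contribute to the within-arm change and, if their effect is the same in both arms, cancel in a between-arm comparison. The last two rows do not cancel.

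**How often the within-arm test could mislead (illustration)**

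Inputs from the documents: n = 62 per arm (Section 8) and significance level 0.05 (Section 7). Assumed: a two-sided test, independent children, normally distributed changes, baseline/follow-up correlation r, a shared improvement of d SDs of the score in both arms, and a method effect of zero.

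- SD of change = SD × √(2(1 − r)). At r = 0.5 this equals the SD of the score.
- Noncentrality of the paired t-test = √n × d / √(2(1 − r)). At r = 0.5 and d = 0.3: √62 × 0.3 = 7.874 × 0.3 = 2.36.
- The critical value on 61 degrees of freedom is 2.00. Rejection probabilities come from the noncentral t distribution.

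| Shared improvement | r = 0.3 | r = 0.5 | r = 0.7 |
|---|---|---|---|
| 0.1 SD | 10% | 12% | 17% |
| 0.2 SD | 26% | 34% | 52% |
| 0.3 SD | 50% | 64% | 85% |
| 0.5 SD | 91% | 97% | 99.9% |

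**The between-arm comparison under the same conditions**

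In a simulation of 20,000 trials at r = 0.5, an independent-samples t-test on change rejected in 4.9% to 5.1% of trials for shared improvements of 0.2, 0.3 and 0.5 SD.

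Section 8 carries the baseline value forward for the 4 intervention and 2 control children lost to follow-up. With that rule applied, the within-arm figures are 32%, 62% and 96% at 0.2, 0.3 and 0.5 SD, and the between-arm figures are 4.8% to 5.2%. The imputation rule does not change the picture.

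**The case against.** The strongest reply is that the controlled question is already the main one. Both general objectives and the first hypothesis compare the arms, the plaque and gingival results in Section 8 are between-group, and nowhere do the documents draw an efficacy conclusion from a within-arm P value. That stands, and it makes this a matter of what the specific objectives can support, not a defect in the main comparison.

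It is also fair to say that the rejection rates above are not false rejections of the second hypothesis as written. If shared components lower plaque, plaque after does differ from plaque before. The error would lie in attributing the change to the method. And the rates depend on assumed inputs: at a shared improvement of 0.1 SD they are only 10% to 17%.

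Three stronger readings are tempting, and the documents do not support them.

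- *Regression to the mean explains the change.* Entry used no plaque or gingivitis threshold, and Experimental Design says that all fifth graders of the two schools took part. Without selection on a high baseline score, the group mean is not expected to regress.
- *The plan prescribes an unpaired test for before/after data.* Section 7 describes a t-test between groups, in an unclear sentence, and is silent on before/after data. The supportable statement is that no analysis is named for the specific objectives.
- *Using the control arm isolates the method.* It does not. Weekly reinforcement went to the intervention arm only, and one school was allocated to each arm by coin flip, so contact time and school remain tied to the method.

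**Conclusion.** The point holds with limited impact. A significant before/after change in the Modified Circular arm cannot support a conclusion about the method, because the shared co-interventions could produce it, and Section 7 gives these objectives no stated analysis. With no method effect and r = 0.5, assumed shared improvements of 0.2 to 0.5 SD give a significant within-arm result in about 34% to 97% of trials, against about 5% for the between-arm test of change. The within-arm range depends on the size of the shared improvement and the correlation, neither of which the documents give. The 5% also requires children to be treated as independent, which one school per arm does not guarantee.

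A reader might infer that the study lacks a controlled comparison or that its reported between-group results are undermined by this point. Neither follows: the general objectives, the first hypothesis and Section 8 all compare the arms.

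**What to change.** 1. Base any conclusion about the method under the specific objectives and second hypothesis on the between-arm difference in follow-up Plaque Index and Gingival Index, adjusted for each child's baseline value. Name this analysis in Section 7.
2. Report before/after change in both arms as paired mean differences with 95% confidence intervals, described as descriptive. Draw no efficacy conclusion from a within-arm P value.
3. Because results are already reported, label the adjusted comparison as supplementary rather than rewriting the hypotheses as if they had been planned that way.
4. State that this removes only the shared components, and that weekly reinforcement and the single school per arm remain confounded with the method.
5. Reconcile Participants and setting, which describes weekly reinforcement sessions of about 20 minutes, with the Data collection procedure, which describes weekly observation with nothing repeated or added to the intervention.

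Cost: one additional analysis of data already collected, and wording in Sections 5 to 8. No new data are needed.

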## 6. Research Procedures

### Participants and setting

One hundred and twenty four students from two state elementary school in Yogyakarta, Indonesia participated in this study. The age of the participants were between 10 and 12 years old including males and females students. All of the participants were fifth graders from Caturtunggal IV State Elementary School and Babarsari State Elementary School. To be eligible to participate in this study, each participants met the criteria including: students with age 10 to 12 years old and willing as well as permitted by the parents/guardian to join thorough the study. The exclusion criterias were not being discovered from them, that were being diagnosed having developmental disorder, using orthodontic appliances, and using antiseptic mouthwash for daily use.

Caturtunggal IV State Elementary School and Babarsari State Elementary School are the government's schools that are placed in the same cluster in one sub-district. These two schools have the similar characteristics in social-economy, number of students, and

the type of school based on the data and recommendation from Education and Culture Office of Sleman District, Yogyakarta, Indonesia. The examinations were done in the terrace in front of the classes to get the sufficient lighting. The training session was done in the class and the schoolyard. Examination and training each lasted approximately 15 minutes and 60 minutes. The examinations were done two times; before and after training with a distance of one month. While the training session were given one time each group after baseline examination. The reinforcement sessions were given to the intervention group once a week in a month after the training session. The reinforcement sessions lasted approximately 20 minutes for each session.

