#### Materials and Equipment

The materials being used in training session were posters, dental model, tooth brush, rinsing glass, and water bucket. The examiner collected the data using probe, mouth-mirror, microbrush, disclosing solution, kidney-basin, cotton roll, mask, gloves, rinsing glass, bucket, table, and chairs. The data of the examination and interview was collected using examination forms, questionnaire, and a pen, while the tooth brushing video was recorded using smartphone and the data was written in observational sheet. The materials for reinforcement sessions were dental model, tooth brush, rinsing glass, bucket, and mirror. Additionally, child size tooth brush and tooth paste were given for each participant.

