### Experimental Design

The research was using a quasi-experimental study design. Data were gathered from two groups of subjects. This research was a single-blind study which the examiner will be blinded to the allocation of subjects.

This study began with selecting two elementary schools in the same district in Yogyakarta, Indonesia, that have similarity in socio-economic status and the number of the students based on the data and recommendation of Technical Education Service Unit of Yogyakarta. The schools met the criteria that was not under any plans of getting other interventions of dental health program during one month intervention period of this study. All of the fifth graders of the selected schools participated the study. With the coin flipping method, a school was allocated to be intervention group and the other was being the control group. The participants had been informed about the purpose of the study, the procedure, and the right to continue or withdrawn without any penalties. The participants had given consent to follow the study.

The study began with the baseline data collection. Then it continued with the training for the participants about improving the oral hygiene. In this stage, the intervention group was demonstrated and instructed to brush their teeth using Modified Circular method, while the control group was not given any instruction to brush their teeth using a specific tooth brushing method and asked to brush their teeth using the way they brushed every day. The period of intervention was started after training and lasted for one month. In intervention period, intervention group was observed once a week to ensure that they brushed their teeth correctly using Modified Circular method. Finally the evaluation was implemented after 1 month of intervention.

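### The accounts of the weekly contact conflict; and on any of them, contact in one arm only and one school per arm mean that the group difference cannot be attributed to brushing method alone

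*Combined protocol and SAP*

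**What the plan says.** All references are to the combined protocol and SAP.

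**Weekly contact.** Four places in section 6 bear on it.

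- Participants and setting: "The reinforcement sessions were given to the intervention group once a week in a month after the training session", and "The reinforcement sessions lasted approximately 20 minutes for each session".
- Materials and Equipment: "The materials for reinforcement sessions were dental model, tooth brush, rinsing glass, bucket, and mirror".
- Experimental Design: "In intervention period, intervention group was observed once a week to ensure that they brushed their teeth correctly using Modified Circular method".
- Data collection procedure, step 4: "Intervention group were observed once a week to make sure that they did Modified Circular method well without any repetition or addition of intervention".

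No section describes weekly contact for the control group.

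**What the arms shared.** Step 4 gives both groups a training course, motivation, the same instruction on brushing frequency and duration, and a supplied brush and toothpaste. Controls were told to keep brushing in their usual way.

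**Allocation.** Under Experimental Design: "With the coin flipping method, a school was allocated to be intervention group and the other was being the control group".

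**Comparison and analysis.** The general objectives (section 5) and the hypotheses (section 6, Dependent Variables and Data Collection) compare children using one brushing method with children using the other. Section 7 compares the groups by t-test. Section 8 reports a significant difference in plaque at follow-up.

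**The concern.** There are two linked points.

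First, the reader cannot tell what the intervention was. A weekly session that reinforces technique on a dental model and a weekly observation that adds nothing are different interventions, and someone wishing to repeat the study would not know which to deliver.

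Second, the arms differ in more than brushing method. If one group is seen every week and the other is not, a difference in plaque may come from the technique, from the attention and supervision, or from both. Because each arm is one school, it may also come from the schools. At stake is what the trial can conclude: read as one method against another, the result would claim more than the design supports.

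**Working it through.** The documents give no figure to reproduce on this point. The check is a comparison of the texts, followed by simple arithmetic on contact time.

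**1. Do the accounts agree?**

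| Section 6 heading | Described as | Length | Group |
|---|---|---|---|
| Participants and setting | reinforcement, weekly | about 20 min | intervention |
| Materials and Equipment | reinforcement, with dental model, brush, glass, bucket and mirror | not given | not given |
| Experimental Design | observation to ensure correct technique | not given | intervention |
| Data collection procedure, step 4 | observation, nothing repeated or added | not given | intervention |

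The first two rows belong together. The dental model, brush, rinsing glass and a bucket also appear among the training-session materials, which suggests some re-teaching. The fourth row appears to exclude that. The third fits either account. The conflict is therefore between the fourth row and the first two.

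**2. Does the attribution problem depend on that conflict?**

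- On the reinforcement account, the arms differ in method and in weekly teaching contact.
- On the observation account, the arms differ in method and in weekly attention.
- On both, they also differ in school.

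So it does not. Method, weekly contact and school coincide completely: every intervention child has one level of all three and every control child the other. A t-test between the groups estimates their combined contrast. Covariate adjustment could not separate them, because none of the three varies within an arm as described.

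**3. How much extra contact?**

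Inputs: about 20 minutes per session (Participants and setting). The number of sessions is not stated; weekly for a month suggests four, and I assume a range of 3 to 5.

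Extra contact = sessions × 20 minutes:

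- 3 × 20 = 60 minutes
- 4 × 20 = 80 minutes
- 5 × 20 = 100 minutes

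No length is given for the observation, so no minutes follow from that account.

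**4. Can this be put as a ratio between arms?**

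Only with a label, because the answer depends on what is counted. Training length is itself given two ways: "Examination and training each lasted approximately 15 minutes and 60 minutes" and "children in each group were given 2 hours for tooth brushing training course". This discrepancy concerns both arms.

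- Training plus weekly sessions only, 60-minute training: (60 + 60)/60 = 2.0 to (60 + 100)/60 = 2.7.
- Training plus weekly sessions only, 120-minute training: (120 + 60)/120 = 1.5 to (120 + 100)/120 = 1.8.
- Adding the two 15-minute examinations that both arms had (30 minutes): 150/90 = 1.7 to 190/90 = 2.1 with 60-minute training, and 210/150 = 1.4 to 250/150 = 1.7 with 120-minute training.

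Interview and video time, of unstated length in both arms, would lower the ratios further. I therefore carry forward only the 60 to 100 extra minutes.

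**The case against.** **The accounts may not conflict.** A brush, glass, bucket and mirror suit observed brushing, and ruling out repetition could mean only that the training course was not given again. This narrows the conflict to the term reinforcement and the dental model. It does not remove the need to say what was delivered.

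**Follow-up support belongs to teaching a technique.** Usual brushing needs no such support, and a taught method against usual habit is a recognisable pragmatic contrast. That is fair. But the objectives and hypotheses do not describe a package, so the reader has to be told that it is one.

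**The documents make little causal claim.** The study is labelled quasi-experimental, there is no discussion section, and the results report group differences without attributing them. This stands and limits the charge: the fault lies in how the comparison is framed and in the absence of a caveat, not in a stated false conclusion.

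**Shared elements and similar schools narrow the gap.** Both arms had motivation, the same brushing instruction and the same supplies, and the schools were chosen for similarity. These reduce other differences but leave the weekly contact.

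**Stronger readings to avoid.** A reader might infer that weekly contact produced the plaque difference; the documents give neither size nor direction for such an effect. A reader might infer that controls were certainly never visited; the documents describe no such contact, which is not a statement that there was none. A reader might also take the significant gingival result as a follow-up finding; that is likely, but the Gingival Index paragraph of section 8 gives no time point for it, so only the plaque result is treated here as a stated follow-up difference.

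**Conclusion.** Both points hold. The sections on weekly contact are inconsistent and must be reconciled; this review takes no position on which account is right. Independently of that, the between-group comparison cannot attribute a difference to the brushing method alone, because weekly contact is described for one arm only and each arm is one school. It would be wrong to infer that the conflict in the text causes the attribution problem: that problem would remain after the text was put right, unless contact proved equal in both arms, and even then the school difference would stay.

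The size is 60 to 100 minutes of extra contact (80 with four sessions). This rests on the reinforcement account and on the assumption of 3 to 5 sessions. It measures exposure and is not an effect size. The point should be fixed because it changes what the trial can be said to show.

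**What to change.** 1. Reconcile Participants and setting, Materials and Equipment, Experimental Design and Data collection procedure, so that they state once what weekly contact each arm actually received: its content, number and length, and whether the control group had any.
2. Leave the objectives and hypotheses as they are. Add to Experimental Design, and beside the plaque and gingival results in section 8, a sentence such as:

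> *The between-group difference reflects training in the Modified Circular method together with the weekly contact as delivered and any difference between the two schools; it cannot be attributed to the brushing method alone.*

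The cost is wording only, with no new data or analysis. The downside is a narrower claim: the result becomes a contrast of a training package plus school, not an effect of the method.
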